**1.0 STS Factors (continued)**

Factor	Definition
Cardiogenic shock	A sustained (>30 min) episode of hypoperfusion evidenced by systolic blood pressure <90 mm Hg and/or, if available, cardiac index <2.2 L/min per square meter determined to be secondary to cardiac dysfunction and/or the requirement for parenteral inotropic or vasopressor agents or mechanical support (eg, IABP, extracorporeal circulation, VADs) to maintain blood pressure and cardiac index above those specified levels. Note: Transient episodes of hypotension reversed with IV fluid or atropine do not constitute cardiogenic shock. The hemodynamic compromise (with or without extraordinary supportive therapy) must persist for at least 30 min.
Resuscitation	Patient required cardiopulmonary resuscitation before the start of the operative procedure which includes the institution of anesthetic management. Capture resuscitation timeframe: within 1 hour or 1-24 hours pre-op
Incidence	
Indicate if this is the patient's:
 
 
• first surgery
 
• first re-op surgery
 
• second re-op surgery
 
• third re-op surgery
 
• fourth or more re-op surgery.
 
 
Surgery is defined as cardiothoracic operations (heart or great vessels) surgical procedures performed with or without cardiopulmonary bypass (CPB). Also include lung procedures utilizing CPB or tracheal procedures utilizing CPB. Reoperation increases risk due to the presence of scar tissue and adhesions.

**1.0 STS Factors (continued)**

Factor	Definition
Cardiac presentation on admission	
Indicate the patient’s cardiac symptoms at the time of this admission.
 
No Symptoms: No Symptoms, no angina.
 
Stable Angina: Angina without a change in frequency or pattern for the prior 6 weeks. Angina is controlled by rest and/or oral or transcutaneous medications.
 
Unstable Angina: There are three principal presentations of unstable angina: 1. Rest angina (occurring at rest and prolonged, usually >20 minutes); 2. New-onset angina (within the past 2 months, of at least Canadian Cardiovascular Society Class III severity); or 3. Increasing angina (previously diagnosed angina that has become distinctly more frequent, longer in duration, or increased by 1 or more Canadian Cardiovascular Society class to at least CCS III severity).
 
–Non-ST Elevation MI (Non- STEMI): The patient was hospitalized for a non-ST elevation myocardial infarction (STEMI) as documented in the medical record. Non-STEMIs are characterized by the presence of both criteria:
 
 
a. Cardiac biomarkers (creatinine kinase-myocardial band, Troponin T or I) exceed the upper limit of normal according to the individual hospital’s laboratory parameters with a clinical presentation which is consistent or suggestive of ischemia. ECG changes and/or ischemic symptoms may or may not be present.
 
b. Absence of ECG changes diagnostic of a STEMI
 
 
–ST Elevation MI (STEMI): The patient presented with a ST elevation myocardial infarction (STEMI) or its equivalent as documented in the medical record. STEMIIs are characterized by the presence of both criteria:
 
 
a. ECG evidence of STEMI: New or presumed new ST segment elevation or new left bundle branch block not documented to be resolved within 20 minutes. ST segment elevation is defined by new or presumed new sustained ST-segment elevation at the J-point in two contiguous electrocardiogram (ECG) leads with the cutoff points: <math>\geq 0.2</math> mV in men or <math>\geq 0.15</math> mV in women in leads V2-V3 and/or <math>\geq 0.1</math> mV in other leads and lasting greater than or equal to 20 minutes. If no exact ST-elevation measurement is recorded in the medical chart, physician’s written documentation of ST elevation or Q waves is acceptable. If only one ECG is performed, then the assumption that the ST elevation persisted at least the required 20 minutes is acceptable. Left bundle branch block (LBBB) refers to new or presumed new LBBB on the initial ECG.
 
b. Cardiac biomarkers (creatinine kinase-myocardial band, Troponin T or I) exceed the upper limit of normal according to the individual hospital’s laboratory parameters a clinical presentation which is consistent or suggestive of ischemia.
 
 
Angina equivalent
 
Other: Presentation/symptom not listed above.


**1.0 STS Factors (continued)**

Factor	Definition
Status of the procedure	
Elective: The patient's cardiac function has been stable in the days or weeks prior to the operation. The procedure could be deferred without increased risk of compromised cardiac outcome.
 
Urgent: Procedure required during same hospitalization in order to minimize chance of further clinical deterioration. Examples include but are not limited to: Worsening, sudden chest pain, CHF, acute myocardial infarction (AMI), anatomy, IABP, unstable angina (USA) with intravenous (IV) nitroglycerin (NTG) or rest angina.
 
Emergent: Patients requiring emergency operations will have ongoing, refractory (difficult, complicated, and/or unmanageable) unrelenting cardiac compromise, with or without hemodynamic instability, and not responsive to any form of therapy except cardiac surgery. An emergency procedure is one in which there should be no delay in providing operative intervention. The patient's clinical status includes any of the following: a. Ischemic dysfunction (any of the following): (1) Ongoing ischemia including rest angina despite maximal medical therapy (medical and/or IABP)); (2) Acute Evolving Myocardial Infarction within 24 hours before surgery; or (3) pulmonary edema requiring intubation. b. Mechanical dysfunction (either of the following): (1) shock with circulatory support; or (2) shock without circulatory support.
 
Emergent Salvage: The patient is undergoing CPR en route to the OR or prior to anesthesia induction or has ongoing ECMO to maintain life.

[figure not shown]
**2.0 Other Factors Not Captured by Traditional Risk Score**

Co-morbidity	Definition/Criteria
Porcelain aorta or severely atherosclerotic aorta	Heavy circumferential calcification or severe atheromatous plaques of the entire ascending aorta extending to the arch such that aortic cross-clamping is not feasible.
Frailty	Slowness, weakness, exhaustion, wasting and malnutrition, poor endurance and inactivity, loss of independence Criteria: 
 
• 5 meter walking time
 
• Grip strength
 
• BMI <20 kg/m^2 and/or weight loss 5 kg/yr
 
• Serum albumin <3.5 g/dL
 
• Cognitive impairment or dementia
 

Sever liver disease/cirrhosis	Any of the following: 
 
• Child-Pugh class C
 
• MELD score ≥10
 
• Portal-caval, spleno-renal, or transjugular intrahepatic portal shunt
 
• Biopsy proven cirrhosis with portal hypertension or hepatocellular dysfunction
 

Hostile chest	Any of the following or other reasons that make redo operation through sternotomy or right anterior thoracotomy prohibitively hazardous: 
 
• Abnormal chest wall anatomy due to severe kyphoscoliosis or other skeletal abnormalities (including thoracoplasty, Potts' disease)
 
• Complications from prior surgery
 
• Evidence of severe radiation damage (eg, skin burns, bone destruction, muscle loss, lung fibrosis or esophageal stricture)
 
• History of multiple recurrent pleural effusions causing internal adhesions
 

IMA or other critical conduit(s) crossing midline and/or adherent to posterior table of sternum	A patent IMA graft that is adherent to the sternum such that injuring it during re-operation is likely. A patient may be considered extreme risk if any of the following are present: 
 
• The conduit(s) are radiographically indistinguishable from the posterior table of the sternum.
 
• The conduit(s) are radiographically distinguishable from the posterior table of the sternum but lie within 2-3 mm of the posterior table.
 

Severe pulmonary hypertension Severe right ventricular dysfunction	Primary or secondary pulmonary hypertension with PA systolic pressures greater than 2/3 of systemic pressure Criteria as defined by the guidelines (eg, TAPSE <15mm, RV end-systolic area >20 cm  )

**APPENDIX IV: RESHEATH AND RECAPTURE DEFINITIONS**

The following definitions are applicable to the data elements on the Implant eCRF that address the use of the resheath and recapture feature.

Resheath attempt	An attempt to intentionally resheath only a portion of the TAV (including the frame) into the capsule of the delivery catheter (eg, with the intent to reposition of the valve during deployment).
Recapture attempt	An attempt to intentionally fully resheath the entire TAV (including the frame) into the capsule of the delivery catheter until there is no gap between capsule and the tip (eg, with the intent to enable re-crossing of the aortic valve or retrieval of the system, Figure 14D).
Reposition	Repositioning of the TAV proximally or distally before final deployment
Retrieve	Retrieval of a partially deployed TAV

**Figure 10. (A)** Between 0 and 1/3 of the valve length outside of the capsule **(B)** between 1/3 and 2/3 of the valve length outside of the capsule **(C)** Point of no return: capsule marker in alignment with the spindle marker **(D)** Full recapture: entire valve resheathed into the capsule until there is no gap between capsule and the tip.

**APPENDIX V: DEFINITIONS: SAFETY ENDPOINTS AND EFFICACY EVENTS**

Definitions of adverse events to be evaluated as clinical safety endpoints, other related complications, and efficacy events are provided in Sections 1.0, 2.0, and 3.0, respectively. The CEC and site investigators will code safety endpoint events according to these definitions, using the associated code list provided on Section 4.0, Event Code List.

**1.0 Safety Endpoint Definitions**

Mortality	
Cardiovascular mortality	Any of the following criteria: 
 
1) Death due to proximate cardiac cause (eg, myocardial infarction, cardiac tamponade, worsening heart failure)
 
2) Death caused by non coronary vascular conditions such as neurological events, pulmonary embolism, ruptured aortic aneurysm, dissecting aneurysm, or other vascular disease
 
3) All procedure-related deaths, including those related to a complication of the procedure or treatment for a complication of the procedure
 
4) All valve-related deaths including structural or nonstructural valve dysfunction or other valve-related adverse events
 
5) Sudden or unwitnessed death
 
6) Death of unknown cause
 

Non-cardiovascular mortality	Any death in which the primary cause of death is clearly related to another condition (eg, trauma, cancer, suicide).

**1.0 Safety Endpoints (continued)**

Myocardial Infarction	
Periprocedural MI (≤72 h after the index procedure)	New ischemic symptoms (eg, chest pain or shortness of breath), or new ischemic signs (eg, ventricular arrhythmias, new or worsening heart failure, new ST-segment changes, hemodynamic instability, new pathological Q-waves in at least 2 contiguous leads, imaging evidence of new loss of viable myocardium or new wall motion abnormality) AND Elevated cardiac biomarkers (preferable CK-MB) within 72 h after the index procedure, consisting of at least 1 sample post procedure with a peak value exceeding 15x as the upper reference limit for troponin or 5x for CK-MB. If cardiac biomarkers are increased at baseline (>99th percentile), a further increase in at least 50% post procedure is required AND the peak value must exceed the previously stated limit.
Spontaneous MI (>72 h after the index procedure)	Any of the following criteria: 
 
1) Detection of rise and/or fall of cardiac biomarkers (preferably troponin) with at least 1 value above the 99th percentile URL, together with the evidence of myocardial ischemia with at least 1 of the following:                             
 
• Symptoms of ischemia
 
• ECG changes indicative of new ischemia (new ST-T changes or new left bundle branch block (LBBB))
 
• New pathological Q-waves in at least 2 contiguous leads
 
• Imaging evidence of a new loss of viable myocardium or new wall motion abnormality
 
 
 
2) Sudden, unexpected cardiac death, involving cardiac arrest, often with symptoms suggestive of myocardial ischemia, and accompanied by presumably new ST elevation, or new LBBB, and/or evidence of fresh thrombus by coronary angiography and/or at autopsy, but death occurring before blood samples could be obtained, or at a time before the appearance of cardiac biomarkers in the blood.
 
3) Pathological findings of an acute myocardial infarction
 

**1.0 Safety Endpoints (continued)**

Stroke and TIA

Diagnostic criteria
 
1) Acute episode of a focal or global neurological deficit with at least 1 of the following:
 
 
• change in the level of consciousness
 
• hemiplegia, hemiparesis
 
• numbness or sensory loss affecting 1 side of the body
 
• dysphasia or aphasia
 
• hemianopia
 
• amaurosis fugax
 
• other neurological signs or symptoms consistent with stroke
 
 
Stroke: duration of a focal or global neurological deficit <math>\geq 24</math> h; OR <math>< 24</math> h if available neuroimaging documents a new hemorrhage or infarct; OR the neurological deficit results in death
 
TIA: duration of a focal or global neurological deficit <math>< 24</math> h, any variable neuroimaging does not demonstrate a new hemorrhage or infarct
 
2) No other readily identifiable non-stroke cause for the clinical presentation (eg, brain tumor, trauma, infection, hypoglycemia, peripheral lesion, pharmacological influences), to be determined by or in conjunction with the neurologist
 
3) Confirmation of the diagnosis by at least 1 of the following:
 
 
• Neurologist or neurosurgical specialist
 
• Neuroimaging procedure (CT scan or brain MRI), but stroke may be diagnosed on clinical grounds alone
 

Stroke Definitions
 
Disabling stroke: an mRS score of 2 or more at 90 days and an increase in at least 1 mRS category from an individual's pre-stroke baseline
 
Non-disabling stroke: an mRS score of <math>< 2</math> at 90 days or one that does not result in an increase in at least 1 mRS category from an individual's pre-stroke baseline

Stroke Classifications
 
Ischemic: an acute episode of focal cerebral, spinal, or retinal dysfunction caused by infarction of the central nervous system tissue
 
Hemorrhagic: an acute episode of focal or global cerebral or spinal dysfunction caused by intraparenchymal, intraventricular, or subarachnoid hemorrhage
 
Undetermined: insufficient information to allow categorization as ischemic or hemorrhagic

**1.0 Safety Endpoints (continued)**

Bleeding Complications	
Life-threatening or disabling bleeding	1) Fatal bleeding ( BARC type 5 ) OR 2) Bleeding in a critical organ, such as intracranial, intraspinal, intraocular, or pericardial necessitating pericardiocentesis, or intramuscular with compartment syndrome ( BARC type 3b and 3c ) OR 3) Bleeding causing hypovolemic shock or severe hypotension requiring vasopressors or surgery ( BARC type 3b ) OR 4) Overt source of bleeding with drop in hemoglobin $\geq 5$ g/dL or whole blood or packed red blood cells (RBCs) transfusion $\geq 4$ units* ( BARC type 3b )
Major bleeding ( BARC type 3a )	1) Overt bleeding either associated with a drop in the hemoglobin level of at least 3.0 g/dL or requiring transfusion of 2 or 3 units of whole blood/RBC, or causing hospitalization or permanent injury, or requiring surgery AND 2) Does not meet criteria of life-threatening or disabling bleeding
Minor bleeding ( BARC type 2 or 3a, depending on the severity )	Any bleeding worthy of clinical mention (eg, access site hematoma) that does not qualify as life-threatening, disabling, or major
*Given one unit of packed RBC typically will raise hemoglobin concentration by 1 g/dL, an estimated decrease in haemoglobin will be calculated; BARC: Bleeding Academic Research Consortium  ; RBC: red blood cell	

Note: With respect to blood transfusions, it is critical to acknowledge that a bleeding complication has to be the result of overt bleeding and cannot be adjudicated based on blood transfusions alone.

Acute Kidney Injury (up to 7 days post procedure)	
Stage 1	1) Increase in serum creatinine to 150%-199% (1.5-1.99 x increase compared with baseline) OR increase of $\geq 0.3$ mg/dL ( $\geq 26.4$ mmol/L) OR 2) Urine output $< 0.5$ mL/kg/h for $> 6$ but $< 12$ h
Stage 2	1) Increase in serum creatinine to 200%-299% (2.0-2.99 x increase compared with baseline) OR 2) Urine output $< 0.5$ mL/kg/h for $> 12$ but $< 24$ h
Stage 3	1) Increase in serum creatinine to $\geq 300\%$ ( $> 3$ x increase compared with baseline) OR serum creatinine of $\geq 4.0$ mg/dL ( $\geq 354$ mmol/L) with an acute increase of at least 0.5 mg/dL (44 mmol/L) OR 2) Urine output $< 0.3$ mL/kg/h for $\geq 24$ h OR 3) Anuria for $\geq 12$ h

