Key Exclusion Criteria	
 
• Bicuspid aortic valve identified by echocardiography, MDCT, or Magnetic Resonance Imaging
 
• Significant ascending aortopathy
 

Subject Evaluation (Main trial)	
 
• Clinical assessment at pre and post-procedure, discharge, 30 days, 6 months, 1 year, 18 months, 2 years, 3 years, 4 years, 5 years, 7 years and 10 years
 
• Transthoracic echo at pre and post-procedure, 30 days, 6 months, 1 year, 2 years, 3 years, 4 years, 5 years, 7 years and 10 years
 
• Multi-Detector Computed Tomography at pre-procedure
 
• Blood samples at pre- and post-procedure, discharge, and 30 days
 
• 12-lead ECG at pre- and post-procedure, discharge, and 30 days
 

	
 
Adverse event review will be conducted at all visits and via telephone for the 6, 8, and 9 year follow-up visits
 

Subject Evaluation (LTI Sub-study)	
 
MDCT at 30 days and one year post-implantation
 

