### 2.5.2 Secondary Safety Endpoints

- The rate of the composite of death, disabling stroke, life-threatening bleed, major vascular complication, or AKI (II or III) at 30 days
- The rate of new permanent pacemaker implantation at 30 days
- The rate of prosthetic valve endocarditis at one year
- The rate of prosthetic valve thrombosis at one year
- The rate of all stroke (disabling and non-disabling) at one year
- The rate of life-threatening bleeding at one year
- The rate of valve-related dysfunction requiring repeat procedure at one year

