#### **18 hours to 7 days Post Procedure (Device Success)**

- TTE (for device success)
- Creatinine
- Adverse Events

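### The AKI staging table leaves longer oliguria without a stage and prints its SI creatinine limits in the wrong unit; separately, the schedule guarantees only one creatinine in the seven-day AKI window

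*Protocol*

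**What the plan says.** Protocol Section 2.5.2 lists as a secondary safety endpoint "The rate of the composite of death, disabling stroke, life-threatening bleed, major vascular complication, or AKI (II or III) at 30 days". SAP Section 6.7 compares it between arms as a proportion. Stages II and III are Stages 2 and 3 of the table in Appendix V, Section 1.0, headed "Acute Kidney Injury (up to 7 days post procedure". The introduction to Appendix V has the Clinical Events Committee (CEC) and the sites code events by these definitions.

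The urine-output rules are:

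- Stage 1: "Urine output $< 0.5$ mL/kg/h for $> 6$ but $< 12$ h"
- Stage 2: "Urine output $< 0.5$ mL/kg/h for $> 12$ but $< 24$ h"
- Stage 3: "Urine output $< 0.3$ mL/kg/h for $\geq 24$ h OR 3) Anuria for $\geq 12$ h"

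The creatinine rules are ratios to baseline, plus absolute limits in mg/dL with a bracketed SI value. Stage 1 has a rise of 0.3 mg/dL (26.4 mmol/L). Stage 3 has "serum creatinine of $\geq 4.0$ mg/dL ( $\geq 354$ mmol/L" in brackets, with an acute rise of at least 0.5 mg/dL (44 mmol/L). Stage 2 is a ratio only.

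In Section 3.3.9, creatinine appears before the procedure, once at the visit headed "18 hours to 7 days Post Procedure (Device Success", and at 30 days. Table 2 agrees. The synopsis, under subject evaluation for the main trial, says "Blood samples at pre- and post-procedure, discharge, and 30 days" without naming the tests.

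**The concern.** A staging rule should not score a longer episode below a shorter one, and a bracketed unit conversion should equal the value beside it. The AKI table fails on both counts. AKI II or III is one of the composite's five components, so a subject who falls through the gap, and has no other component event, is counted as event-free. Sites in Europe, Canada, Australia, New Zealand and Japan also use the table, and any that report creatinine in SI units will look to the bracketed limits.

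The creatinine criteria can be applied only to values that were measured. The detailed schedule guarantees one value in a seven-day window and leaves its timing open across most of that window. The synopsis describes a different set of blood samples, so the guaranteed minimum is itself unclear.

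**Working it through.** **1. Urine output.** Applying the three printed rules literally gives:

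| Output (mL/kg/h) | 8 h | 12 h | 13 h | 23.9 h | 24 h | 48 h |
|---|---|---|---|---|---|---|
| 0 (anuria) | 1 | 3 | 3 | 3 | 3 | 3 |
| 0.1 or 0.25 | 1 | none | 2 | 2 | 3 | 3 |
| 0.3, 0.4 or 0.49 | 1 | none | 2 | 2 | none | none |

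There are two holes: 0.3 to below 0.5 mL/kg/h for 24 h or more, and exactly 12 h of non-anuric oliguria. Output below 0.3 mL/kg/h for 24 h or more, and anuria for 12 h or more, are correctly staged.

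**2. Units.** The molar mass of creatinine (C4H7N3O) is 113.12 g/mol, a physical constant and not a figure in the documents. The conversion is mmol/L = mg/dL × 10 / 113.12.

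| mg/dL | mmol/L | micromol/L | Printed (mmol/L) | Printed / true |
|---|---|---|---|---|
| 0.3 | 0.0265 | 26.5 | 26.4 | 996 |
| 4.0 | 0.3536 | 353.6 | 354 | 1001 |
| 0.5 | 0.0442 | 44.2 | 44 | 996 |

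The printed numerals reproduce within 1% if the unit is micromol/L. Taken as mmol/L, 354 would be about 4004 mg/dL.

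**3. What a literal mmol/L reading would cost.** The absolute limits could never be met, so only the ratios would apply. The 0.3 mg/dL limit is Stage 1 and lies outside the composite. For the Stage 3 limit, let the peak be P ≥ 4.0 mg/dL and the baseline b. The event leaves II/III only if P/b < 2, that is b > P/2 ≥ 2.0 mg/dL. At P = 4.0, a baseline up to 1.33 is still Stage 3 by ratio (4.0/1.33 = 3.01). A baseline from 1.34 to 2.0 falls from Stage 3 to Stage 2 and stays in the composite. Section 3.3.5.2 sets no renal limit, so subjects with a baseline above 2.0 can enter, but the documents do not say how many.

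**4. Schedules side by side.**

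| Time | Synopsis | Section 3.3.9 and Table 2 |
|---|---|---|
| Pre-procedure | blood samples | blood count, creatinine |
| 12 to 24 h | – | no blood test |
| 18 h to day 7 | post-procedure blood samples | creatinine |
| Discharge or day 7, whichever is first | blood samples | INR, only if on a vitamin K antagonist |
| 30 days | blood samples | creatinine; INR if on a vitamin K antagonist |

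The synopsis list fits neither test. Creatinine has no discharge sample, and INR continues through five years while the synopsis list stops at 30 days. No urine-output collection is scheduled.

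**5. Does timing within 18 h to day 7 matter?** This is an illustration on assumed inputs: a one-compartment model with volume 42 L and an abrupt, sustained fall of GFR to a fraction f of its baseline GFR0 (mL/min). The ratio to baseline is r(t) = 1/f − (1/f − 1)·exp(−kt), with k = GFR0·f·1.44/42 per day. It reaches 2.0 at t = ln[(1/f − 1)/(1/f − 2)]/k.

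- GFR0 50, f 0.40: k = 0.686. r is 1.60 at 18 h and 1.74 at 24 h; it reaches 2.0 at ln(3)/0.686 = 1.60 days, or 38.5 h.
- GFR0 80, f 0.45: 33.1 h. GFR0 80, f 0.40: 24.0 h.
- GFR0 80, f 0.30: about 16 h.
- f 0.20: about 20 h (GFR0 50) or 13 h (GFR0 80).

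A compliant 18 h sample can thus fall before or after the crossing, depending on the severity of the injury and baseline function.

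**The case against.** Much can be said in defence of the plan.

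- **Urine gap.** Someone oliguric beyond 24 h has already passed 12 h, so an adjudicator could reasonably assign Stage 2. That stands as common sense, but it is a private repair of a rule that sites and the CEC are told to follow. The definitions are attributed to VARC II, so rewording them could cost some comparability.
- **Units.** The mg/dL limits stand beside the SI values, and the printed mmol/L values are physiologically impossible, so the slip is visible. A micro sign lost when the PDF was read also cannot be excluded. Both stand, and step 3 of the working shows how little depends on it.
- **Sampling.** A reader might infer that AKI staging rests on a single creatinine. The documents do not support that. Appendix V does not restrict staging to scheduled samples, adverse events are reported and followed to resolution (Section 3.3.26.2), and the CEC adjudicates with source documents (Sections 3.3.26.2 and 3.3.27). The modelled subject at 1.60 times baseline at 18 h is already Stage 1, hence reportable and followed. What remains is that the CEC sees only events that investigators report, and a rise that nobody sampled may not be reported.
- **Discharge creatinine.** A reader might take the synopsis to promise one. It names no test, so the point is only that the passages disagree.
- **Direction of bias.** It is tempting to say that earlier discharge after TAVR hides more AKI and so favours TAVR. The schedule is the same in both arms, and the documents give no length of stay, sampling frequency or AKI rate by arm. Neither the direction nor the existence of a difference can be established.
- **Scheduled samples only.** An analysis confined to scheduled creatinines might seem to equalise the arms. It would not: one arm could be sampled at 18 h and the other on day 6, both within window, and genuine events would be discarded.

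**Conclusion.** The staging table is wrong as written in two places and should be corrected. The urine-output gap follows directly from the printed inequalities. The unit error is a factor of about 1000, subject to checking the signed original for a micro sign, and on a literal reading it removes a stage II/III event only when baseline creatinine exceeds 2.0 mg/dL. On sampling, the supportable statement is narrower: the detailed schedule guarantees one creatinine in the AKI window, at an open time, and the synopsis does not match it.

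The number of affected events cannot be calculated, because the documents give no AKI rate. The effect on the composite is probably small. The composite is a secondary safety endpoint outside the hierarchical testing (Protocol Section 3.3.3.7, SAP Section 6.9), and the primary endpoint and sample size do not depend on it. The creatinine model rests on an assumed volume, GFR and pattern of injury; it shows only that sample timing can matter.

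**What to change.** 1. Define Stage 2 urine output as below 0.5 mL/kg/h for 12 h or more and not meeting Stage 3. With Stages 1 and 3 unchanged, this closes both holes. Note it as a clarification of the attributed VARC II definition, and apply it to both arms, including events already adjudicated.
2. Change mmol/L to micromol/L in all three places.
3. Reconcile the synopsis, the discharge list in Section 3.3.9 and Table 2, naming the tests meant.
4. Record from source the highest available creatinine and its date through day 7 in both arms, and apply the creatinine criteria to that value.
5. Tabulate the timing of those samples by arm, so that readers can judge whether ascertainment was comparable.

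The cost is two lines of definition, two eCRF fields, some abstraction and one table. The recorded AKI rate may rise slightly. Because the continued-access addendum concludes the randomized phase, a new blood draw would come too late for those subjects, so item 4 relies on existing records. The addendum's own 30-day composite has no AKI component and needs no change on this point.
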